## 10. ADVERSE EVENTS

The Investigator is responsible for the detection and documentation of events meeting the criteria and definitions detailed below. This responsibility may be delegated to a member of the research team. Assessment of events may be delegated to other suitably qualified physicians in the research team who are trained in recording and reporting adverse events (AEs).

Investigational Medicinal Product (IMP) is defined as any active substance or placebo being studied or used as a reference in the trial. This section also applies to medicinal products that are not the active substance or placebo, but are used as a concomitant medication to the IMP or as a rescue/escape medicine for preventative, diagnostic or therapeutic reasons. These are referred to as non Investigational Medicinal Products (NIMPs).

Full details of contraindications and side effects that have been reported following administration of the IMP can be found in the relevant SmPC in the ISF.

Participants should be instructed to contact their Investigator (or member of the study team) at any time after consenting to join the trial if any symptoms develop. All AEs that occur after joining the trial and result in interaction with a healthcare professional must be reported in detail in the CRF or AE form. In the case of an AE, the Investigator should initiate the appropriate treatment according to their medical judgment. Participants with AEs present at the last visit must be followed up until resolution of the event.

## 10.1 DEFINITIONS

An **adverse event** (AE) is any untoward medical occurrence in a clinical trial participant which does not necessarily have a causal relationship with an investigational medicinal product (IMP).

An **adverse reaction** (AR) is any untoward or unintended response to an IMP which is related to any dose administered to that participant.

An **unexpected adverse reaction** (UAR) is an adverse reaction that is not consistent with the applicable product information for the IMP, e.g. the Investigator Brochure (IB) for a non licensed IMP or the SmPC for a licensed product.

A **serious adverse event** (SAE), **serious adverse reaction** (SAR) or **suspected unexpected serious adverse reaction** (SUSAR) is any AE, AR or UAR that at any dose:

- results in death;
- is life threatening\* (i.e. the participant was at risk of death at the time of the event; it does not refer to an event which hypothetically might have caused death if it were more severe);
- requires hospitalisation^ or prolongation of existing hospitalisation;
- results in persistent or significant disability or incapacity;
- is a congenital anomaly or birth defect.

\* Life-threatening in the definition of an SAE or SAR refers to an event where the participant was at risk of death at the time of the event. It does not refer to an event which hypothetically might have caused death if it were more severe.

^Any hospitalisation that was planned prior to randomisation will not meet SAE criteria. Any hospitalisation that is planned post randomisation, will meet the SAE criteria. The only exception to this is the **elective** admission for surgery relating to the participants wrist fracture. This **does not** require to be reported as an SAE.

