Alendronic acid is a bisphosphonate that inhibits osteoclastic bone resorption. Bisphosphonates such as alendronic acid bind to calcified bone matrix and suppress bone remodelling primarily as the result of their inhibitory effects on osteoclast activity, although inhibitory effects on bone formation may also occur. Since alendronic acid inhibits bone turnover it could theoretically affect fracture healing as restoration of the original shape and strength of a bone following fracture depends on remodelling of callus by osteoclasts and on the formation of new bone by osteoblasts. Pre-clinical studies have not shown any adverse effects in fracture healing and on the contrary have shown positive effects of bisphosphonates on the strength of fracture callus. However, observational studies in man have raised the possibility that bisphosphonate therapy may increase the risk of fracture non-union.

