## 10.6 REGULATORY REPORTING REQUIREMENTS

The ACCORD Research Governance & QA Office is responsible for Pharmacovigilance reporting on behalf of the co-sponsors (Edinburgh University and Lothian Health Board).

The ACCORD Research Governance & QA Office has a legal responsibility to notify the regulatory competent authority and relevant ethics committee (Research Ethics Committee (REC) that approved the trial). Fatal or life threatening SUSARs will be reported no later than 7 calendar days and all other SUSARs will be reported no later than 15 calendar days after ACCORD is first aware of the reaction.

ACCORD will inform Investigators at participating sites of all SUSARs and any other arising safety information.

An Annual Safety Report will be submitted to the regulatory competent authority and main REC listing all SARs and SUSARs.

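### The SAE exemption in 10.1 for elective wrist-fracture surgery is not limited to initial treatment, so elective re-operation for impaired healing is not reportable as an SAE on the hospitalisation criterion

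*Protocol*

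**What the plan says.** The footnote to the hospitalisation criterion in Protocol 10.1 sets three rules.

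- Admissions planned before randomisation: "Any hospitalisation that was planned prior to randomisation will not meet SAE criteria".
- Admissions planned afterwards count as SAEs, with one carve-out, namely an elective "admission for surgery relating to the participants wrist fracture".
- An admission within that exception need not be reported as an SAE.

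The footnote is attached to one seriousness criterion only, hospitalisation "or prolongation of existing hospitalisation". The others, including an event that "results in persistent or significant disability or incapacity", carry no such exemption.

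Three other sections bear on the point. Section 1.1 notes that "observational studies in man have raised the possibility that bisphosphonate therapy may increase the risk of fracture non-union", and 1.2 says that a finding of delayed healing could lead clinicians to withdraw the drug or defer starting it. Section 10.5 requires SAEs to be reported immediately or within 24 hours. Section 10.6 states: "An Annual Safety Report will be submitted to the regulatory competent authority and main REC listing all SARs and SUSARs".

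**The concern.** Exempting planned surgery from SAE reporting is unremarkable when the surgery has nothing to do with the drug hypothesis. Here it may have a great deal to do with it. The trial asks whether alendronic acid impairs healing of a distal radial fracture, and elective admission to operate on a fracture that has failed to heal, lost position or healed badly is a clinical consequence of impaired healing. The exemption does not separate that operation from the initial fixation of a fresh fracture.

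What is at stake is safety surveillance while the trial runs. Under 9.2 no formal interim efficacy analysis is intended, and a safety issue is the only ground on which the DMC could recommend stopping early. Safety data are therefore the route by which an excess of re-operations in one arm would be acted on during the trial, and the exemption takes elective re-operations out of one part of those data.

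**Working it through.** The protocol states no figure on this point, so the check is a reading of the sections against each other.

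**1. When the exception has any effect.** Admissions planned before randomisation are already excluded by the preceding sentence of the footnote. The exception therefore operates only on wrist surgery decided after randomisation.

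**2. What that surgery can be.** Section 4.2 admits displaced fractures and fractures treated by external fixation or by open reduction and internal fixation. Under 5.5.1 and 5.5.2, randomisation may precede the safety blood results, and the first dose may follow randomisation by up to 7 days (within 14 days of fracture). Initial fixation decided after randomisation, possibly before any tablet is taken, is thus within the exception. So is elective surgery months later for delayed union, non-union, lost position or malunion, because the wording limits neither time nor indication. No other section brings the later operations back in.

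**3. What follows for a later elective re-operation.** Take a participant admitted electively at about week 16 for surgery on a non-united radius, with no other seriousness criterion met. The hospitalisation criterion does not apply, so by that route:

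- no report to the pharmacovigilance office within 24 hours is required (10.5);
- a case judged drug-related is an AR rather than a SAR, so it cannot become a SUSAR and be unblinded as 10.4 provides;
- it does not appear in the annual report, which lists only SARs and SUSARs (10.6).

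**4. What still captures the event.**

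- Emergency admissions are outside the exception, and the life-threatening and disability criteria are untouched (10.1).
- The Chief Investigator may upgrade an AE to an SAE, SAR or SUSAR (10.4).
- AE recording continues: "All AEs that occur after joining the trial and result in interaction with a healthcare professional must be reported in detail" (section 10). Participants are asked about hospital admissions at every visit (10.2). The record includes onset date, severity, causality, treatment required and outcome (10.3), and causality is assessed for non-serious events too (10.4.2).
- Telephone calls at weeks 16 and 24 collect AEs (7.2.10).

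**5. Whether the endpoints cover it.** The primary endpoint is radiographic healing at week 4 (2.2.1), which cannot show a later failure. Table 7–1 schedules no radiograph between week 8 and week 26, a gap of 26 − 8 = 18 weeks. Malunion is read on the week 26 film (2.2.2), so a malunion corrected surgically before then could be read as absent. Neither non-union nor re-operation is listed in 2.2 or Table 7–1.

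**6. Size.** The protocol gives no re-operation or non-union rate. Purely as an assumed range for elective wrist re-operation after randomisation: 500 × 0.01 = 5 and 500 × 0.05 = 25 admissions. These counts treat every operation as an elective admission that meets no other seriousness criterion, so at the assumed rates they are upper limits.

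**The case against.** The strongest reply is that this is a drafting matter with little consequence. The exemption has an ordinary purpose: initial fixation arranged shortly after randomisation would otherwise generate SAE forms of no value. Failed healing is measured directly by blinded central reading, with radiographs at weeks 2, 4, 6, 8 and 26, and function, pain and CRPS-I are compared between arms. A re-operation can still be recorded as an AE with causality and treatment, and the wording waives a duty to report rather than forbidding a report.

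Most of this stands, and it rules out several stronger conclusions that a reader might draw.

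- That re-operation for failed healing can never enter serious-event reporting. It can, through the routes in step 4 of the check.
- That the exception catches only surgery decided while the participant is on blinded drug. It also covers initial fixation decided after randomisation and before the first dose.
- That re-operation is the harm the trial is designed to detect. The design targets radiographic healing at week 4, with malunion at week 26 as a secondary endpoint.
- That the DMC would not see these events. Its terms of reference are in a separate document (12.4), and nothing in the protocol says that it reviews only SAEs. The CRF is not shown either.

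The reply does not remove the gap. Upgrading is discretionary and depends on someone noticing the case. A non-serious AE entry does not trigger the reporting in 10.5 and 10.6. A legitimate purpose for initial fixation does not explain why the wording also reaches later operations.

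**Conclusion.** The point holds in a limited form. As written, 10.1 leaves an elective re-operation for impaired healing outside the hospitalisation criterion and, by that route, outside expedited reporting and the annual list. The gap matters more here than in most trials because impaired healing is the suspected drug effect, re-operation is not otherwise a defined item, and safety is the only ground for a DMC stopping recommendation. It is partial because the other routes to seriousness and ordinary AE recording remain.

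The number of events affected cannot be estimated from the protocol; the range of 5 to 25 rests wholly on the assumed 1% to 5%. No analysis, endpoint or stated figure is shown to be wrong. This is a worthwhile, inexpensive improvement to safety capture and not an error that must be corrected before the trial can be relied on.

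**What to change.** Either of two changes would do.

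1. In 10.1, limit the exemption to surgery that is part of the initial fracture treatment plan documented at baseline. Any later elective admission for surgery on the trial fracture then follows the general rule for hospitalisations planned after randomisation.
2. Keep the exemption, but require every later operation on the trial fracture to be recorded on the CRF with its date and indication, and tabulate these by arm for the DMC.

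The first needs one sentence in an amendment and a modest number of extra SAE forms, some of them for early surgery on displaced fractures. The second adds CRF entries and one table, but leaves the events outside 24-hour reporting. Neither alters treatment, visits or the efficacy analysis.

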## 10.2 DETECTING AEs AND SAEs

All AEs and SAEs must be recorded from the time a participant commences study drug until the last study visit.

Participants will be asked about the occurrence of AEs/SAEs at every visit during the study. Open-ended and non-leading verbal questioning of the participant will be used to enquire about AE/SAE occurrence. Participants will also be asked if they have been admitted to hospital, had any accidents, used any new medicines or changed concomitant medication regimens. If there is any doubt as to whether a clinical observation is an AE, the event will be recorded.

AEs and SAEs may also be identified by support departments e.g. laboratories. Abnormal laboratory values and test results should only be noted as adverse events if they are symptomatic or require treatment (e.g. blood transfusion for low haemoglobin).

## 10.3 RECORDING AEs AND SAEs

When an AE/SAE occurs, it is the responsibility of the Investigator to review all documentation (e.g. hospital notes, laboratory and diagnostic reports) related to the event. The Investigator should then record all relevant information in the CRF and on the SAE form (if the AE meets the criteria of serious).

Information to be collected includes dose, type of event, onset date, Investigator assessment of severity and causality, date of resolution as well as treatment required, investigations needed and outcome.

## 10.4 ASSESSMENT OF AEs AND SAEs

Seriousness, causality, severity and expectedness should be assessed as though the participant is taking active IMP. Cases that are considered serious, possibly, probably or definitely related to IMP and unexpected (i.e. SUSARs) should be unblinded.

The Investigator is responsible for assessing each AE. This may be delegated to other suitably qualified physicians in the research team who are trained in recording and reporting AEs.

The Chief Investigator (CI) may not downgrade an event that has been assessed by an Investigator as an SAE or SUSAR, but can upgrade an AE to an SAE, SAR or SUSAR if appropriate.

### 10.4.1 Assessment of Seriousness

The Investigator should make an assessment of seriousness as defined in Section 10.1.

### 10.4.2 Assessment of Causality

The Investigator must make an assessment of whether the AE/SAE is likely to be related to the IMP according to the definitions below.

All AEs/SAEs judged as having a reasonable suspected causal relationship (e.g. possibly, probably, definitely) to the IMP will be considered as related to the IMP (ARs/SARs).

Where non Investigational Medicinal Products (NIMPs) e.g. rescue/escape drugs are given: if the AE is considered to be related to an interaction between the IMP and the NIMP, or where the AE might be linked to either the IMP or the NIMP but cannot be clearly attributed to either one of these, the event will be considered as an AR/SAR.

**Unrelated:** where an event is not considered to be related to the IMP.

**Possibly:** although a relationship to the IMP cannot be completely ruled out, the nature of the event, the underlying disease, concomitant medication or temporal relationship make other explanations possible.

**Probably:** the temporal relationship and absence of a more likely explanation suggest the event could be related to the IMP.

**Definitely:** The known effects of the IMP or its therapeutic class, or based on challenge testing, suggest that the IMP is the most likely cause.

Alternative causes such as natural history of the underlying disease, other risk factors and the temporal relationship of the event to the treatment should be considered and investigated. The blind should not be broken for the purpose of making this assessment.

### 10.4.3 Assessment of Severity

The Investigator will make an assessment of severity for each AE/SAE and record this on the CRF or AE form according to one of the following categories:

**Mild:** an event that is easily tolerated by the participant, causing minimal discomfort and not interfering with every day activities.

**Moderate:** an event that is sufficiently discomfoting to interfere with normal everyday activities.

**Severe:** an event that prevents normal everyday activities.

Note: the term 'severe', used to describe the intensity, should not be confused with 'serious' which is a regulatory definition based on participant/event outcome or action criteria. For example, a headache may be severe but not serious, while a minor stroke is serious but may not be severe.

### 10.4.4 Assessment of Expectedness

If an event is judged to be an AR/SAR, the evaluation of expectedness should be made based on knowledge of the reaction and the relevant product information documented in the SmPC.

The event should be classed as either:

**Expected:** the AR is consistent with the toxicity of the IMP listed in the SmPC or IB.

**Unexpected:** the AR is not consistent with the toxicity in the SmPC or the IB.

## 10.5 REPORTING OF SAEs/SARs/SUSARs

Once the Investigator becomes aware that an SAE has occurred in a study participant, the information will be reported to the ACCORD Research Governance & QA Office **immediately or within 24 hours**. If the Investigator does not have all information regarding an SAE, they should not wait for this additional information before notifying ACCORD. The SAE report form can be updated when the additional information is received.

The SAE report will provide an assessment of causality and expectedness at the time of the initial report to ACCORD according to Sections 10.4.2, Assessment of Causality and 10.4.4, Assessment of Expectedness.

The SAE form will be transmitted by fax to ACCORD on **[name]** or may be transmitted by hand to the office.

Where missing information has not been sent to ACCORD after an initial report, ACCORD will contact the Investigator and request the missing information until this is supplied.

All SAE, SAR and SUSAR reports faxed to ACCORD and any follow up information will be retained in the ISF.

## 10.6 REGULATORY REPORTING REQUIREMENTS

The ACCORD Research Governance & QA Office is responsible for Pharmacovigilance reporting on behalf of the co-sponsors (Edinburgh University and Lothian Health Board).

The ACCORD Research Governance & QA Office has a legal responsibility to notify the regulatory competent authority and relevant ethics committee (Research Ethics Committee (REC) that approved the trial). Fatal or life threatening SUSARs will be reported no later than 7 calendar days and all other SUSARs will be reported no later than 15 calendar days after ACCORD is first aware of the reaction.

ACCORD will inform Investigators at participating sites of all SUSARs and any other arising safety information.

An Annual Safety Report will be submitted to the regulatory competent authority and main REC listing all SARs and SUSARs.

## 10.7 FOLLOW UP PROCEDURES

After initially recording an AE or recording and reporting an SAE, the Investigator is required to follow each participant until resolution or death of the participant. Follow up information on an SAE should be reported to the ACCORD office.

AEs still present in participants at the last study visit should be monitored until resolution of the event or until no longer medically indicated.

## 11. PREGNANCY

Pregnancy is not considered an AE or SAE, however, the Investigator must collect pregnancy information for any female participants or female partners of male participants who become pregnant while participating in the study. The Investigator should record the information on a Pregnancy Notification Form and submit this to the ACCORD office within 14 days of being made aware of the pregnancy.

All pregnant female participants and partners of male participants should be followed up until the outcome of the pregnancy.

## **12. TRIAL MANAGEMENT AND OVERSIGHT ARRANGEMENTS**

### **12.1 TRIAL MANAGEMENT GROUP**

The trial will be coordinated by a Project Management Group, consisting of the grantholders (Chief Investigator and Principal Investigator (PI) in Edinburgh), a Trial Manager and coordinating nurse.

The Trial Manager will oversee the study and will be accountable to the Chief Investigator. The Trial Manager will be responsible for checking the CRFs for completeness, plausibility and consistency. Any queries will be resolved by the Investigator or delegated member of the trial team.

A Delegation Log will be prepared for each site, detailing the responsibilities of each member of staff working on the trial. If any changes are made to the Delegation Log during the study an updated copy should be sent to the Clinical Trial Manager at the Central Trial Office.

### **12.2 CENTRAL TRIAL OFFICE**

The Central Trial Office is based in the Edinburgh Clinical Trials Unit (ECTU) and will provide support to each site. The office will be responsible for randomisation, collection of data in collaboration with the research nurses, data processing and analysis.

Publication and dissemination of the study results will be coordinated by ECTU in collaboration with the Chief Investigator and Investigators.

### **12.3 TRIAL STEERING COMMITTEE**

A Trial Steering Committee (TSC) will be established to oversee the conduct and progress of the trial. The terms of reference of the Trial Steering Committee, the draft template for reporting and the names and contact details will be detailed in a separate document.

### **12.4 DATA MONITORING COMMITTEE**

An independent Data Monitoring Committee (DMC) will be established to oversee the safety of participants in the trial. The terms of reference of the Data Monitoring Committee and the names and contact details will be detailed in a separate document.

### **12.5 INSPECTION OF RECORDS**

Investigators and institutions involved in the study will permit trial related monitoring and audits on behalf of the sponsor, REC review, and regulatory inspection(s). In the event of an audit or monitoring, the Investigator agrees to allow the representatives of the sponsor direct access to all study records and source documentation. In the event of regulatory inspection, the Investigator agrees to allow inspectors direct access to all study records and source documentation.

